8.1.3 QUANTITATIVE MRI STRUCTURAL, MICROSTRUCTURAL AND METABOLIC BIOMARKERS OF ACUTE BRAIN INJURY

Our goal is to obtain baseline and follow-up brain MRI in approximately half of the study participants (55 subjects in each study arm). For additional information, refer to MRI Manual.

At sites recruiting infants into the MRI portion of the study, infants will be quieted by swaddling and feeding before the MRI study. O₂ saturation, heart rate and temperature will be monitored and recorded throughout the scan. All infants will be protected from MRI scanner noise by the use of ear wax, and mini muffs (Natus MiniMuffs Noise Attenuators). MRI acquisition protocols will be standardized and field-tested across all sites in Y1 Q1-3, and MRI calibration studies will be performed to ensure that the MRI scanner properties and parameter settings during the acquisition phase are correct. Conventional MRI studies will be reviewed in a standardized fashion by a pediatric neuroradiologist at each site blinded to study randomization.

All MRI data sets will be processed at the Advanced Pediatric Brain Imaging Research Laboratory (DBRL) at Children's National Medical Center. All quantitative MRI outcome measures are continuous and will be performed by a single investigator masked to randomization. Abnormalities of brain development, maturation, the presence of focal destructive ischemic or hemorrhagic lesions, will be documented.

8.1.4 SALIVARY CAFFEINE LEVELS

Two salivary samples will be obtained for later analysis of caffeine concentrations, the 1st in the NICU 1 week after starting study drug, and the 2nd, which may be either in the hospital or at home by parents, at about 40 weeks + 0 days PMA. All samples will be pre-prandial. Salivary volumes of 200-300 uL will be collected using commercially available kits (Salimetrics, State College, PA) and frozen at -20° C at home and then at -20° C or colder after return to the clinical site research team for bulk analysis at the end of the study. Parents will return the home salivary sample at the same time as their scheduled return to the clinical site at study end. As specified by later shipping instructions, the frozen salivary samples will be batched and shipped on dry ice overnight with the plasma samples using shipping labels that will be provided.

Salivary analyses will be performed by the Biomedical Research Lab at Walter Reed National Military Medical Center. Sample preparation and chromatography will utilize a method validated in our preliminary study.^{89,90} Chromatography will be performed using a Waters Alliance 2695 Separations Module equipped with a Waters 2996 Photodiode Array detector and Waters Symmetry column.

8.1.5 BRIEF INFANT SLEEP QUESTIONNAIRE (BISQ)

The Brief Infant Sleep Questionnaire (BISQ) is a parent-reported questionnaire on infant/toddler sleep over the prior one week. It includes 13 items in three categories (sleep duration, night wakings, and method of falling asleep). The BISQ will be completed by phone during the weekly phone call that is scheduled between 42 weeks 0 days and 42 weeks 6 days, or in person, at study termination if this occurs prior to 42 weeks + 0 days.

8.2 SAFETY AND OTHER ASSESSMENTS

8.2.1 TELEPHONE ASSESSMENT OF STATUS AT HOME

Within 1 – 3 days following hospital discharge to home, and at least weekly thereafter, study site staff will contact families by phone and complete a phone contact log. The phone contact log will document:

- Family questions or concerns
- Assessment of completion of the drug log and issues related to administration or supply of study drug
- Assessment of extent of use of study oximeter (**if applicable**) and any questions, problems or other concerns related to study drug
- Discussion of upcoming study procedures
- Assessment for occurrence of adverse events
- Determination of use of concomitant medications

8.3 ADVERSE EVENTS AND SERIOUS ADVERSE EVENTS

8.3.1 DEFINITION OF ADVERSE EVENTS (AE)

- Adverse event means any untoward medical occurrence associated with the use of an intervention in humans, whether or not considered intervention-related (21 CFR 312.32 (a)).
- Since there will be multiple participating clinical sites, centralized safety oversight will be coordinated by the DCC in conjunction with the ICAF principal investigators.
- The study does not involve an investigational new drug, but is extending the duration of caffeine treatment beyond the customary age of discontinuing caffeine treatment in the NICU. The FDA has deemed the use of caffeine in this study as consistent with prior FDA approval, and has therefore granted an IND Exemption.
- There is no risk in randomizing to placebo; absent enrollment in this study, infants would not be treated with caffeine.

8.3.2 DEFINITION OF SERIOUS ADVERSE EVENTS (SAE)

An adverse event (AE) or suspected adverse reaction is considered "serious" if, in the view of either the investigator or sponsor, it results in any of the following outcomes: death, a life-threatening adverse event, inpatient hospitalization or prolongation of existing hospitalization, or a persistent or significant incapacity or substantial disruption of the ability to conduct normal life functions. Important medical events that may not result in death, be life-threatening, or require hospitalization may be considered

serious when, based upon appropriate medical judgment, they may jeopardize the participant and may require medical or surgical intervention to prevent one of the outcomes listed in this definition.

Note that for the purpose of this study, delaying discharge of an infant related to achieving a specified 'spell-free' number of days shall NOT be considered a 'prolongation of existing hospitalization' for the purpose of categorizing an event as a serious adverse event.

8.3.3 CLASSIFICATION OF AN ADVERSE EVENT

8.3.3.1 SEVERITY OF EVENT

The following guidelines will be used to describe severity.

- **Mild** – Events require minimal or no treatment and do not interfere with the participant's daily activities.
- **Moderate** – Events result in a low level of inconvenience or concern with the therapeutic measures. Moderate events may cause some interference with functioning.
- **Severe** – Events interrupt a participant's usual daily activity and may require systemic drug therapy or other treatment. Severe events are usually potentially life-threatening or incapacitating. Of note, the term "severe" does not necessarily equate to "serious".

8.3.3.2 RELATIONSHIP TO STUDY INTERVENTION

All adverse events (AEs) will have their relationship to study intervention assessed by the clinical site principal investigators based on temporal relationship and clinical judgment. The degree of certainty about causality will be graded using the categories below:

- **Definitely Related** – There is clear evidence to suggest a causal relationship, and other possible contributing factors can be ruled out. The clinical event occurs in a plausible time relationship to study intervention administration and cannot be explained by concurrent disease or other drugs or chemicals.
- **Probably Related** – There is evidence to suggest a causal relationship, and the influence of other factors is unlikely. The clinical event occurs within a reasonable time after administration of the study intervention, is unlikely to be attributed to concurrent disease or other drugs or chemicals.
- **Potentially Related** – There is some evidence to suggest a causal relationship (e.g., the event occurred within a reasonable time after administration of the trial medication). However, other factors may have contributed to the event (e.g., the participant's clinical condition, other concomitant events). An AE may rate as "possibly related" soon after discovery, but it can be flagged as requiring more information and later be upgraded to "probably related" or "definitely related", as appropriate.
- **Unlikely to be related** – A clinical event whose temporal relationship to study intervention administration makes a causal relationship improbable and other drugs or underlying disease provides plausible explanations (e.g., the participant's clinical condition, other concomitant treatments).
- **Not Related** – The AE is completely independent of study intervention administration, and/or evidence exists that the event is definitely related to another etiology. The alternative, definitive etiology must be documented by the clinical care team.

8.3.3.3 EXPECTEDNESS

- The clinical site principal investigators will be responsible for determining whether an adverse event (AE) is expected or unexpected. An AE will be considered unexpected if the nature, severity, or frequency of the event is not consistent with the well-established risk information previously described for caffeine.
- Expected AE for caffeine treatment can include tachycardia, feeding intolerance, jitteriness. However, no significant AE are expected since all enrollees will have previously tolerated routine caffeine treatment at systemic concentrations similar to those achieved in this study.

8.3.4 TIME PERIOD AND FREQUENCY FOR EVENT ASSESSMENT AND FOLLOW-UP

- The occurrence of an adverse event (AE) or serious adverse event (SAE) may come to the attention of clinical care personnel as part of routine NICU care, or by research staff or parents.
- All AEs including local and systemic reactions not meeting the criteria for SAEs will be captured on the appropriate case report form (CRF). Information to be collected includes event description, time of onset, clinician's assessment of severity, relationship to study product (assessed only by those with the training and authority to make a diagnosis), and time of resolution/stabilization of the event.
- All AEs occurring while on study must be documented appropriately regardless of relationship. All AEs will be followed to adequate resolution.
- Any medical condition that is present at the time that the participant is enrolled will be considered as baseline and not reported as an AE. However, if the study participant's condition deteriorates at any time during the study, it will be recorded as an AE.
- Changes in the severity of an AE will be documented to allow an assessment of the duration of the event at each level of severity to be performed. AEs characterized as intermittent require documentation of onset and duration of each episode.
- Designated study site research staff will record all reportable events occurring in the NICU starting from when informed consent is obtained until the last day of study participation (for non-serious AEs) or 30 days (for SAEs) after the last day of study participation. NOTE: Last day of study participation may be any of the following:
 - end-of-study visit
 - follow-up MRI visit
 - Lost-to-follow-up determination date
- After discharge home, research staff will query parents at least weekly about the occurrence of AE/SAEs since the last contact. Events will be followed for outcome information until resolution or stabilization.

8.3.5 ADVERSE EVENT REPORTING

AEs and SAEs will be documented in the source records and recorded on the eCRFs using accepted medical terms and/or the diagnoses that accurately characterize the event. When a diagnosis is known, the AE term recorded on the eCRF will be the diagnosis rather than a constellation of symptoms. The clinical site principal investigators or

their designee will assess all AEs for seriousness, relationship to investigational product, severity, expectedness, and other possible etiologies. When an event has not resolved by study closure, it will be documented on the AE eCRF as “ongoing”.

The timeframe for the collection of AEs and SAEs is noted above in section 8.3.4.

8.3.6 SERIOUS ADVERSE EVENT REPORTING

All SAEs must be reported promptly (within 24 hours) to the study DCC, whether or not the event is considered related to study product. Further, the clinical site principal investigators should comply with relevant clinical study site IRB requirements on reporting SAEs.

Clinical site principal investigators must submit additional information as soon as it is available on the SAE report form. The study DCC will report unexpected SAEs associated with the use of the drug as required.

Clinical site principal investigators must follow all relevant regulatory requirements as well as specific policy regarding the timely reporting of SAEs to the study DCC and the clinical study site IRB.

Reporting to the study DCC does not fulfill the clinical site principal investigator's duty to report all unanticipated problems involving risk to human subjects or others to the IRB. The clinical site principal investigators will notify the clinical study site IRB and ICAF principal investigators.

- Any AE considered serious by the clinical site principal investigator or an ICAF principal investigator, or which meets the definition of an SAE included in **Section 8.3.2, Definition of Serious Adverse Events** must be submitted on an SAE form to the Data Coordinating Center (DCC).
- The DSMB will receive expedited notification of all SAEs, even if not thought to be related to study intervention.
- All serious adverse events (SAEs) will be followed until satisfactory resolution or until the clinical site principal investigator deems the event to be chronic or the participant is stable. Other supporting documentation of the event may be requested by the Data Coordinating Center (DCC) and should be provided as soon as possible.

8.3.7 REPORTING EVENTS TO PARTICIPANTS

Not Applicable

8.3.8 EVENTS OF SPECIAL INTEREST

- Although rare, infants born at ≤ 30 weeks gestation and discharged home are at risk for an apparent life-threatening event (ALTE, or brief resolved unexpected event, BRUE) or for sudden unexpected infant death (SUID)

- Infants enrolled in this study are at no greater risk, and perhaps at even less risk, for such events than infants not enrolled

8.3.9 REPORTING OF PREGNANCY

Not applicable

8.4 UNANTICIPATED PROBLEMS

8.4.1 DEFINITION OF UNANTICIPATED PROBLEMS (UP)

Federal regulations (45 CFR Part 46/32 CFR 219) require that unanticipated problems involving risks to subjects or others be promptly reported to the IRB. These events encompass a broader category of events than SAEs and may include issues such as problems with loss of control of subject data or the investigational product; adverse psychological reactions; or breach of confidentiality. Risks to others (e.g., program personnel) must also be reported.

The Office for Human Research Protections (OHRP) considers unanticipated problems involving risks to participants or others to include, in general, any incident, experience, or outcome that meets all of the following criteria:

- Unexpected in terms of nature, severity, or frequency given (a) the research procedures that are described in the protocol-related documents, such as the Institutional Review Board (IRB)-approved research protocol and informed consent document; and (b) the characteristics of the participant population being studied;
- Related or possibly related to participation in the research (“possibly related” means there is a reasonable possibility that the incident, experience, or outcome may have been caused by the procedures involved in the research); and
- Suggests that the research places participants or others at a greater risk of harm (including physical, psychological, economic, or social harm) than was previously known or recognized.

8.4.2 UNANTICIPATED PROBLEM REPORTING

The clinical site principal investigators will report unanticipated problems (UPs) occurring from the time the informed consent form is obtained through 30 days after the last day of study participation to the clinical study site Institutional Review Board (IRB) and to the Data Coordinating Center (DCC)/ICAF principal investigators. The UP report will include the following information:

- Protocol identifying information: protocol title and number, Clinical site principal investigator's name, and the IRB project number;
- A detailed description of the event, incident, experience, or outcome;
- An explanation of the basis for determining that the event, incident, experience, or outcome represents an UP;
- A description of any changes to the protocol or other corrective actions that have been taken or are proposed in response to the UP.

To satisfy the requirement for prompt reporting, UPs will be reported using the following timeline:

- UPs will be reported to the clinical study site IRB and to the DCC and PI/Co-PI within 1 business day of the investigator becoming aware of the event.

All UPs should be reported to appropriate institutional officials (as required by an institution's written reporting procedures), the supporting agency head (or designee), and the Office for Human Research Protections (OHRP) promptly after the clinical study site IRB's receipt of the report of the problem from the clinical site principal investigators.

9 STATISTICAL CONSIDERATIONS

9.1 STATISTICAL HYPOTHESES

Primary Objective 1: Compare the extent of **IH** exposure, from randomization through 42 weeks + 6 days PMA (within each gestational week and overall), in infants randomized to extended caffeine treatment to infants assigned to receive placebo. *We hypothesize that caffeine will reduce the extent of IH compared to placebo, and that this caffeine effect will persist through 42 weeks PMA.*

Primary Objective 2: Compare changes in a panel of inflammation-related cytokines and chemokines, from enrollment to the target age of 38 weeks + 0 days PMA, in infants randomized to extended caffeine treatment to infants assigned to receive placebo. *We hypothesize that continuing caffeine treatment will be associated with less inflammation compared to placebo.*

Primary Objective 3: Compare changes in quantitative MRI structural, microstructural and metabolic biomarkers of acute injury, from enrollment to 43-46 weeks PMA, in infants randomized to extended caffeine treatment to infants assigned to receive placebo. *We hypothesize that continued caffeine treatment compared to placebo will be associated with 1) greater white matter microstructural organization, 2) improved neuronal metabolism, and 3) greater regional brain volume.*

Secondary Objective 1: Examine the association between salivary caffeine concentrations and **IH** outcomes at the one week post randomization and 40 weeks + 0 days PMA assessments. *We hypothesize that those with higher salivary caffeine concentrations will have less severe IH outcomes.*

Secondary Objective 2: Determine whether caffeine effects on changes in inflammatory or MRI biomarkers from baseline to follow-up are mediated by caffeine-related reduced **IH**. *We hypothesize that caffeine effects on changes in inflammatory or MRI biomarkers will be at least partially mediated by reduced IH.*

9.2 SAMPLE SIZE DETERMINATION

Sample Size: We will randomize 220 infants, **110 in each treatment group**, with ≥ 100 infants/group available for final analyses. Sample size considerations focus on PMA week-specific differences between the extended caffeine vs. placebo infants for our primary outcome of #sec/day $< 90\%$ saturation from 36 to 42 weeks PMA. Preliminary data showed effect sizes at 37 and 38 weeks PMA of 0.87 and 0.73. With the decline in **IH** with increasing age, we expect that 1) the caffeine effect may decline and 2) moderate effects will be needed to achieve a meaningful reduction in **IH** to 42 weeks PMA. Therefore, we consider an effect size of 0.50 to represent a meaningful detectable difference between groups. Final samples of $n=100$ per group gives 82% power to detect this effect, testing at the overall 2-tailed .05 level with a familywise Type I error correction adjusting for multiple testing across weeks. Secondary outcomes of **#IH** events and **#sec < 80% saturation/day** showed effect sizes at 38 weeks PMA of 0.73 and 0.46 in our pilot data.

9.3 POPULATIONS FOR ANALYSES

The intention-to-treat (ITT) population will consist of all randomized subjects.

The modified intention-to-treat (mITT) population will include all subjects who took at least one dose of study drug and who have data available for efficacy outcomes.

The safety population will consist of all randomized subjects who receive a dose of study drug.

9.4 STATISTICAL ANALYSES

9.4.1 GENERAL APPROACH

Statistical significance will be declared at the two-sided $p < 0.05$ level; when appropriate, correction for multiple comparisons will be employed. For analyses of primary and secondary objectives, we will adjust for demographic and clinical differences. When employed, tests for interaction will at the 0.1 alpha level. Results will be presented through measures of effect and 95% confidence intervals. If lost to follow-up exceeds the 10% anticipated under sample size considerations, multiple imputation on the intent-to-treat population will be used for sensitivity analyses that account for missing data. All computations will be performed using the latest available version of SAS®.

Demographic variables and subject characteristics will be summarized descriptively by treatment assignment and overall. Continuous parameters will be summarized using descriptive statistics (N, mean, median, standard deviation, minimum and maximum value). Categorical demographic parameters, such as gender, will be summarized as a percentage of the population.

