5. Includes documentation of tracking information, and parent training including: use of oximeter, drug administration, use of drug administration log, salivary sample collection, communication expectations and follow-up plans.
6. Weekly phone calls from study staff to parent(s) begin 1- 3 days after hospital discharge and continue through end of study follow up visit. A phone follow-up form will be completed to collect clinical data, adverse events, and document family questions.
7. Sleep Assessment (BISQ) done over the phone with parent at 42 weeks.
8. The end of study visit, which may be done remotely, is targeted for 43 + 6 days, or one week after the last dose of study drug, whichever comes first, but should be completed no later than 46 + 6. Study staff will collect the study drug log, used bottles, unused drug, study oximeter, and frozen salivary sample. Items may be shipped back if the parents opt for a remote visit.
9. Collection of concomitant medications and adverse event monitoring and reporting are continuous throughout study.
10. Home-oximetry will only be performed for subjects enrolled at sites participating in the home-oximetry portion of the study.

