4.4 END OF STUDY DEFINITION

Each subject will be considered to have completed the study after the planned pulse oximeter recording data is completed and inflammatory biomarker samples are provided, and if applicable, has completed the outpatient brain MRI between 43 weeks + 0 days and 46 weeks + 6 days PMA, as shown in the Schedule of Activities (SOA), Section 1.3.

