7.2 PARTICIPANT DISCONTINUATION/WITHDRAWAL FROM THE STUDY

Each study participant may withdraw consent at any time during the study without penalty. In the event a participant is discontinued and thus no longer receiving the study drug, the participant will be asked to continue with follow-up assessment as described below, and not considered withdrawn from the study. If the participant refuses further follow-up, then the participant will be considered to be withdrawn. Counseling about the participant's health will be provided if the participant decides to discontinue participation in the study. Medical advice regarding what is in the best interest of the participant will be provided.

All data collected up to the time of withdrawal will be reported. The End of Study eCRF will be completed, with the reason for withdrawal specified.

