7.3 LOST TO FOLLOW-UP

- A participant will be considered lost to follow-up if he or she fails to return for the end-of-study visit between 43 weeks + 0 days and 46 weeks and 6 days PMA and is unable to be contacted by the study site staff to (1) reschedule the final visit for the brain MRI (if applicable) to be completed by 46 weeks + 6 days, and (2) return all study equipment and supplies within the next 4 weeks.
- If the subject does not return for the final evaluation, the site will attempt to contact the family and reschedule the missed visit within the next 1-4 weeks, counsel the participant on the importance of maintaining the assigned visit schedule, and ascertain if the family wishes to and/or should continue in the study.
- Before a participant is deemed lost to follow-up, the clinical site investigator or designee will make every effort to regain contact with the participant by multiple means or by contacting designated

alternative contacts. These contact attempts will be documented in the participant's medical record or study file.

- Should the participant continue to be unreachable, the participant will be considered to have withdrawn from the study with a primary reason of lost to follow-up.

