8 STUDY ASSESSMENTS AND PROCEDURES

8.1 EFFICACY ASSESSMENTS

8.1.1 OXYGEN SATURATION

Continuous recording of O₂ saturation using the study pulse oximeter is planned for all infants through hospital discharge, **and for the sub-group of infants recruited at hospitals participating in home oximetry recording, will continue through 43 weeks + 6 days PMA (i.e. one week following the last dose of study drug).** The study oximeter will be the Masimo RAD-97, set at the minimum possible averaging time of 2–4 sec and a sampling rate of 1 sec (high resolution). The oximeter will be preset in the sleep lab mode, hence with no “probe off,” “low battery,” or physiologic visual displays or alarms. The internal data storage capacity of the RAD-97 oximeter is sufficient for 28 days of continuous data collection.

Inpatient Phase: During the inpatient phase, the RAD-97 will be a 2nd oximeter, in addition to the one used for standard monitoring in the NICU. Continuous oximeter recordings will be obtained whenever in the NICU. Data will be downloaded from the monitor, and archived by the DCC, at least every 4 weeks while in the NICU and at discharge.

Please note: Some sites may discontinue oximeter recordings at hospital discharge.

Outpatient Phase: **At sites participating in the home oximetry portion of the study,** prior to discharge, the family will be trained in the use of the RAD-97, and will be asked to use the oximeter during all sleep times and quiet awake periods until 43 weeks + 6 days PMA. At home, therefore, we expect at least 8 – 12 hours of use per day, so the memory capacity of the RAD-97 should be sufficient to complete the outpatient phase.

Following discharge, the family will be contacted within the first 2 – 3 days, and then at least weekly to provide support in the use of the study monitor and to support other aspects of the study protocol. As part of their support of the use the monitor at home, study site staff will assess if the use pattern is such that the oximeter memory might be close to capacity, and determine if it is necessary to schedule an additional data download.

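### The lost-to-follow-up trigger for the multiple-imputation sensitivity analysis (9.4.1) does not measure missing primary-endpoint data

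*Combined protocol and SAP*

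**What the plan says.** Section 9.4.1 sets the rule: "If lost to follow-up exceeds the 10% anticipated under sample size considerations, multiple imputation on the intent-to-treat population will be used for sensitivity analyses". The sentence goes on to say that these analyses are meant to account for missing data. It does not cite a definition of lost to follow-up.

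Section 7.3 is the only place that defines the term, and it has two parts. The participant "fails to return for the end-of-study visit between 43 weeks + 0 days and 46 weeks and 6 days PMA" and, in addition, "is unable to be contacted by the study site staff". Section 7.2 treats refusal by a family that can be reached as a separate status: "If the participant refuses further follow-up, then the participant will be considered to be withdrawn". The Schedule of Activities (1.3, footnote 8) loosens the visit itself: "The end of study visit, which may be done remotely", and "Items may be shipped back if the parents opt for a remote visit".

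On oximetry, 8.1.1 warns: "Some sites may discontinue oximeter recordings at hospital discharge". Section 4.4 counts an infant as having "completed the study after the planned pulse oximeter recording data is completed", provided the biomarker samples and any applicable MRI are also done. The synopsis puts most discharges at 34 to 40 weeks PMA. The primary IH outcome is tested week by week, with 9.2 powering weeks 36 to 42.

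Section 9.4.2 admits an infant to the IH analysis with 10 hours of acceptable recording in any one PMA week. Biomarker and MRI analyses require a baseline and follow-up pair. Under Secondary Objective 1, after the exploratory mixed-effects models of IH, 9.4.2 adds that multiple imputation will be used if missing data become a problem. It gives no threshold.

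**The concern.** A trigger for a missing-data analysis should respond to missing data. This one responds to whether a family can be contacted at the end of the study, or at best to whether an infant contributed any usable IH week. Neither tracks the values that the primary tests need.

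The late IH weeks matter most, because the primary hypothesis is that the caffeine effect persists through 42 weeks. At sites without home oximetry, late-week IH exists only for infants still in hospital. Section 8.3.2 recognises that discharge may be delayed to reach a set number of spell-free days, so discharge timing can depend on apnea, which the study drug is meant to affect. It is an inference, not something the documents state, that late-week data could therefore be missing in a way related to outcome and arm. That is the case a sensitivity analysis exists to examine, and under the 9.4.1 rule a complete-case result could be reported without it.

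**Working it through.** **1. The plan's own figures.** The trigger needs more than 0.10 × 220 = 22 infants lost, so at least 23. Section 9.2 does not state 10%. Its allowance is 110 randomized to at least 100 analysed per arm, or 1 − 100/110 = 9.1%. The 82% power is reproduced approximately at the first Holm step: power = Φ(d√(n/2) − z), with d = 0.50, n = 100 per arm and two-sided α = 0.05/7 = 0.00714 for weeks 36 to 42. This gives Φ(3.536 − 2.690) = 80.1%. Six tests give 81.5%.

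**2. What each reading of the trigger counts.**

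| Infant | Lost under 7.3? | Unavailable under 9.2 with the one-week IH rule? |
|---|---|---|
| Site without home oximetry, recorded only until discharge | No | No, if one inpatient week qualifies |
| Reachable family stops home recording, remote final visit | No | No, if one week qualifies |
| Reachable family refuses further follow-up | No (withdrawn under 7.2) | Only if no week qualifies |
| Second blood sample missed or unusable | No | No; 9.2 is built on IH |
| Attends MRI, unsedated scan unusable | No | No; 9.2 is built on IH |

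Each of these infants can lack a primary-endpoint value. Under 7.3 none counts toward the trigger. Under 9.2, only an infant with no qualifying IH week does.

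The mismatch also runs the other way: an infant with a complete biomarker pair counts as lost if the family later becomes unreachable.

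**3. How far apart the two can be.** The documents do not give the share *h* of infants at home-oximetry sites, the share *s* discharged before a given week, or the loss rate *l*. All three are assumptions here. Infants in hospital are taken to have data. Discharged infants have data only if they are at a home-oximetry site and not lost:

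missing = 1 − [(1 − s) + s × h × (1 − l)], with l = 2%.

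For h = 50%: s = 50% gives 1 − (0.50 + 0.245) = 25.5%; s = 100% gives 1 − 0.49 = 51.0%.

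| h | s | Missing that week | Left per arm, 110 × (1 − missing) | Power at α = 0.05/7 |
|---|---|---|---|---|
| 75% | 50% | 13.25% | 95.4 | 78% |
| 75% | 100% | 26.5% | 80.8 | 69% |
| 50% | 50% | 25.5% | 82.0 | 70% |
| 50% | 100% | 51.0% | 53.9 | 46% |
| 25% | 50% | 37.75% | 68.5 | 59% |
| 25% | 100% | 75.5% | 26.9 | 20% |

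At 2%, at most 0.02 × 220 = 4.4 infants are lost, against the 23 needed. If every infant has one qualifying inpatient week, none is unavailable on the 9.2 reading either. The trigger stays off in every row.

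**The case against.** **The 7.3 definition may not be the one intended.** This is fair. Section 9.4.1 points to the sample-size section and not to 7.3, and 7.3 itself ends by recording unreachable families as withdrawn. On the 9.2 reading, withdrawn infants without usable data would count. The one-week rule still leaves late-week gaps uncounted, so the defect does not depend on choosing 7.3.

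**A reader might infer that this is the plan's only protection against missing data.** The documents do not support that. Section 9.4.2 has the second imputation sentence and also plans exploratory mixed-effects models, which can use partial series. Nor does 9.4.1 forbid the analysis below 10%. But the second sentence has no threshold, sits under a secondary objective and does not say whether it covers the primary tests.

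**Most of the illustrated gap is planned non-collection, not dropout.** This also stands. Recording that ends at discharge at some sites is a site-level choice, and randomization is stratified by site. It is first a design and power matter, and would distort the comparison only if discharge timing depends on arm or outcome.

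**A reader might count infants who stop study drug early as missing.** Section 7.2 asks them to continue follow-up. Footnote 8 of 1.3, which brings the final visit forward after the last dose, sits awkwardly with that but does not make them missing. Likewise, remote visits, shipped equipment and recording that stops at discharge do not cause missing biomarker pairs. Those arise from missed or unusable samples.

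**Conclusion.** The concern holds in a limited form. On either reading, the 9.4.1 trigger does not measure missing primary-endpoint data and can stay off when well over 10% of week-specific IH values, biomarker pairs or MRI pairs are absent. The text alone establishes this.

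The size is not established. With 2% lost and half of infants at home-oximetry sites, about 25% to 51% would lack IH data in a late week. Over home-site shares of 25% to 75%, the range is about 13% to 76%. These are illustrations. It would be tempting to conclude that late-week data will be mostly missing, or that the week-specific results will be biased. The documents give no rates from which to conclude either.

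The change should be made, but it concerns a supplementary analysis and does not invalidate the primary one.

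**What to change.** In 9.4.1, replace the lost-to-follow-up trigger with the following.

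- **Reporting.** For each primary endpoint (IH in each PMA week; biomarker pairs; MRI pairs among infants at MRI sites only), give by arm the number of randomized infants without an evaluable value and the reason. Separate planned non-collection (recording ended at discharge at a site without home oximetry; non-MRI site) from unplanned loss.
- **Sensitivity analysis.** Run multiple imputation whatever the lost-to-follow-up rate, among infants for whom the endpoint was planned. MRI is not imputed for infants at non-MRI sites. For IH weeks after discharge, also give a labelled version that includes infants at sites without home oximetry, because being in hospital in a given week is itself a post-randomization event.
- **Model.** Include arm, site, earlier-week IH, on/off study drug and discharge date. Add a delta-adjusted (tipping-point) version, since ordinary imputation does not test missingness that depends on outcome and differs by arm.
- **Scope.** State that this rule also governs the imputation sentence under Secondary Objective 1 in 9.4.2.

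The cost is wording and some programming, with the primary analysis unchanged. Sensitivity results would always be reported, would depend on the model in heavily missing weeks, and may be less favourable. Imputation will not restore lost power.
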